6.6.6 Procedure

The attending emergency physician who sees the patient will report the duration of AECOPD symptoms, medication history, and physical findings (temperature, pulse, oxygen saturation, respiratory rate, abnormal lung sounds and peak expiratory flow rate before and after bronchodilators). The patient was treated according to GOLD initiative, including bronchodilator, and systemic steroid. A sputum sample, a throat swab sample (for bacterial culture) and a nasopharyngeal swab (for respiratory virus – pneumonia panel) are collected. The attending physician will assess and record the sputum colour using the Bronkotest chart (Appendix 8). That patient will be interviewed for CCQ an EQ-5D-5L questionnaire.

Patients randomised to the intervention group will be recommended to have CRP tested and the result will be recorded in the proforma. Medication (including antibiotics) prescription and other management plan will be recorded.

Trial team members will collect healthcare service utilization data, spirometry result, laboratory results and antibiotics prescribed for 12 months before randomization.

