6.6.8 Follow Up

The trial team will aim to contact all participants through telephone call, or audio / video call with instant messaging software and application service such as WhatsApp, WeChat, or Instant Messenger, every week after randomization to follow up CCQ and EQ-5D questionnaires. The patient will be met on video call at 4-weeks post randomization. A copy of Chronic Respiratory Disease Questionnaire, self-administered, standardized (CRQ-SAS) and EQ-5D will be sent to patients for completion and return at 6 months.

Week 1 & Week 3

Follow-up call for *week 1 and 3* (±1 working day): The patient will be interviewed for the symptomatology, CCQ and EQ-5D questionnaires.

Week 4

Clinical follow up at *week 4* (±2 working days) by research clinician for medication consumption, adverse effects, sick leave, diagnosis of pneumonia since the initial encounter, any further CRP tests since the initial encounter, health care consultations, CCQ and EQ-5D. The patient will be required to return to the emergency department to undergo fresh sputum collection, throat swab and nasopharyngeal swab anytime during the day of weekdays before end of week 5. The colour of the sputum specimen will be examined. If the patient defaults the follow up at week 4, the team will contact the patient again and collect as many data items as possible. If the patient is unable to present, follow up call will be performed.

Month 6

At *6-months* post randomisation, the trial team member will examine the patient's medical record for any spirometry results, prescription, and healthcare service utilization. The patient will also be sent a copy of CRQ-SAS and EQ-5D then for self-completion. A text reminder message will be sent through with instant messaging software and application service application. Defaulted patients will be called for interview to collect their responses.

7. Assessment of Efficacy

Mean antibiotic duration (in days) within 28-days for AECOPD after randomization.

8. Assessment of Safety

Adverse Event

Events fulfilling the definition of a serious adverse event (SAE), including death, emergency hospitalization for conditions other than AECOPD, life-threatening medical conditions, (required preventive intervention for) disability or permanent damage, or other serious medical events that occur between randomization and 4-week post randomization will be reported to the trial team as soon as it is detected.

9. Statistics and Data Analysis

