Secondary outcome measures include adverse effects potentially attributable to antibiotics prescribed for the exacerbation, general health status measured by EuroQoI-5D (EQ-5D),

Costs (total HA cost) and cost-effectiveness, Disease-specific, health-related quality of life over time measured using the CRQ-SAS (dyspnoea, fatigue, emotion function, mastery and total scores).

11. Direct Access to Source Data/ Documents

The investigators and the research assistants in the research team will be responsible for data collection of the project. The investigators will permit trial-related monitoring, audits, IRB review, and regulatory inspection(s), providing direct access to source data and documents.

12. Ethics

The trial will be conducted in accordance with the principles originating in the Declaration of Helsinki, and those in Good Clinical Practice. After patients (or relatives/legal representatives) are assessed as suitable for the Trial, all subjects for this study will be provided a consent form describing this study and providing sufficient information for subjects to make an informed decision about their participation in this study. This consent form is submitted with the protocol for review and approval by the Institutional Review Board (IRB) for the study. The formal consent of a subject, using the IRB-approved consent form, must be obtained before that subject is submitted to any study procedure. This consent form must be signed by the subject or legally acceptable surrogate, and the investigator-designated research professional obtaining the consent. The trial will be conducted in accordance with the information and consent forms.

13. Data Handling and Record Keeping

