Primary	To determine whether the addition of a serial CRP levels (with advice on interpretation) to usual care for managing AECOPD leads to a reduction in antibiotic exposure for AECOPD without negatively impacting on COPD health status compared to usual care alone.	Recovery in terms of COPD health status as assessed using the Clinical COPD Questionnaire (CCQ) total scores	2 week
Secondary	To evaluate the effect of serial CRP levels for AECOPD in emergency department on:	Prevalence of potentially pathogenic bacteria cultured from sputum at 4 weeks and the proportion of bacteria that are resistant	4-week
		Prevalence of commensal organisms cultured from sputum at 4 weeks and the proportion of bacteria that are resistant	4-week
		Adverse effects potentially attributable to antibiotics prescribed for the exacerbation	Weekly for 4 weeks
		All-cause antibiotic consumption	During the first 4 weeks post randomisation
			week
		orally administered steroids	4-week
		General health status measured by EuroQol-5D (EQ-5D)	Weekly for 4 weeks
		Primary and secondary care consultations, including hospitalisations	4-week & 6-month
		Costs (total HA cost) and cost-	6 month
		Incidence of pneumonia (measured by patient and medical record)	4-week & 6-momnth
		Disease-specific, health-related quality of life over time measured using the CRQ- SAS (dyspnoea, fatigue, emotion function, mastery and total scores)	6-month

Key: AECOPD acute exacerbation of chronic obstructive pulmonary disease, CCQ Clinical COPD Questionnaire, CRP C-reactive protein point-of-care test, CRQ-SAS Chronic Respiratory Disease Questionnaire, self-administered, standardised

Participant Flow Diagram

CONSORT 2010 Flow Diagram

BRONKOTEST

ERS

Evaluation of sputum colour

Sputum purulence correlates with presence of bacteria and favourable effect of antibiotics

european respiratory society every breath counts

Source: https://www.ersnet.org

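### CRQ-SAS is labelled quality of life over time but is scheduled once, at 6 months, with no baseline; the outcome should be redefined as the 6-month difference and adjusted for baseline CCQ and EQ-5D-5L (minor)

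*Combined protocol and SAP*

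**What the plan says.** The outcome is named in three places: the Study Summary (Section 2), Section 10 and Appendix 5. Section 10 and Appendix 5 word it as "Disease-specific, health-related quality of life over time measured using the CRQ"-SAS, and the Study Summary carries the same label, "health-related quality of life over time measured using the CRQ-SAS (dyspnoea, fatigue, emotion function, mastery and total scores". The only time point in its Appendix 5 row is 6 months.

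The schedule is in Sections 6.6.6 and 6.6.8:

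- Enrolment (6.6.6): "That patient will be interviewed for CCQ an EQ-5D-5L questionnaire". CRQ-SAS is not named.
- Weeks 1 and 3 (6.6.8): "The patient will be interviewed for the symptomatology, CCQ and EQ-5D questionnaires". The week 4 follow-up also lists CCQ and EQ-5D only.
- Month 6 (6.6.8): "The patient will also be sent a copy of CRQ-SAS and EQ-5D then for self-completion".

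Section 9 does not mention CRQ-SAS. It compares continuous outcomes by two-sample t test and names no covariate. It also lists Fisher's exact test for COPD-related health status, which is a separate inconsistency; the t test is taken here as the default for a continuous score.

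**The concern.** Describing an outcome as a course over time implies at least two measurements on the same patient. The schedule provides one. An analyst working from this plan could not produce what the label promises, and would have to decide later what the outcome is and how to compare it.

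CRQ-SAS is the only disease-specific quality-of-life measure planned at 6 months, since CCQ is scheduled only to week 4. A clear definition therefore matters to anyone who wants to know how patients fare after the acute phase. The plan also holds baseline scores that could sharpen the comparison, but it does not say that they will be used.

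**Working it through.** **1. Schedule against label.** Questionnaires named at each contact:

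| Contact | Named | Section |
|---|---|---|
| Enrolment | CCQ, EQ-5D-5L | 6.6.6 |
| Weekly contacts before week 4 | CCQ, EQ-5D | 6.6.8 |
| Week 4 | CCQ, EQ-5D | 6.6.8 |
| Month 6 | CRQ-SAS, EQ-5D | 6.6.8 |

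CRQ-SAS assessments per patient: 0 at enrolment, 0 in weeks 1 to 4, and 1 at month 6. A change score or trajectory needs at least 2, so neither can be derived.

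**2. What baseline adjustment could gain.** The plan gives no effect size, SD or power for CRQ-SAS, so there is no figure of its own to reproduce. Let R be the multiple correlation of baseline CCQ and EQ-5D-5L with 6-month CRQ-SAS. The documents do not give R; 0.3 to 0.7 is assumed. The residual variance factor is 1 − R², and the equivalent sample multiplier is 1/(1 − R²).

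| R | 1 − R² | Variance cut | Sample multiplier |
|---|---|---|---|
| 0.3 | 0.91 | 9% | 1.10 |
| 0.5 | 0.75 | 25% | 1.33 |
| 0.7 | 0.51 | 49% | 1.96 |

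**3. How precise the 6-month comparison already is.** Inputs from the plan: N = 1,184 (Section 2), 1:1 allocation (6.6.2) and significance at 0.05 (Section 9). Assumed: a two-sided test, 80% power, and 0% to 30% of 6-month forms missing. The detectable difference in SD units is √(2/n) × (1.960 + 0.842), with n per arm. Adjustment multiplies it by √(1 − R²).

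With 20% missing, n = 1,184 × 0.8 / 2 = 473.6, and √(2/473.6) × 2.802 = 0.182.

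| Missing | n per arm | Unadjusted | R = 0.3 | R = 0.5 | R = 0.7 |
|---|---|---|---|---|---|
| 0% | 592 | 0.163 | 0.155 | 0.141 | 0.116 |
| 20% | about 473 | 0.182 | 0.174 | 0.158 | 0.130 |
| 30% | about 414 | 0.195 | 0.186 | 0.169 | 0.139 |

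The unadjusted comparison already detects about 0.16 to 0.20 SD. Adjustment shortens that by about 5% at R = 0.3 and 29% at R = 0.7.

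**The case against.** The strongest reply is that this is only a label. No section defines the outcome as a change score or a within-patient slope. Allocation is randomised 1:1, so the difference in 6-month scores is an unbiased estimate of the effect on quality of life at that time. CRQ-SAS is also absent from the secondary objectives in Section 5.2. EQ-5D is collected at enrolment, weekly and at 6 months, so a generic measure with a baseline exists at the late time point. All of this stands, and it is why the severity is minor.

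Three stronger readings are tempting, and the documents do not support them.

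- *A reader might infer that the outcome cannot be analysed, or that without a baseline the comparison is biased.* Randomisation makes the 6-month comparison valid. Only change and trajectory are lost.
- *A reader might infer that the comparison is too imprecise for a null result to mean much.* Under the stated assumptions it detects about 0.18 SD with 20% missing, which is a small difference. Chance imbalance in severity is already reflected in the standard error.
- *A reader might infer that exacerbations between enrolment and 6 months should be accounted for.* They occur after randomisation and may be affected by the intervention, so they belong to the effect being estimated.

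It can also be objected that the time-point diagram and participant flow diagram mentioned in Section 6.6.3 are not shown in the available text, so a baseline CRQ-SAS there cannot be fully excluded. The Appendix 5 table does not settle this alone: it lists CCQ at 2 weeks only, although Section 6.6.6 also collects it at enrolment. The finding rests on Sections 6.6.6 and 6.6.8, which agree with each other.

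**Conclusion.** The mismatch is confirmed in the readable text: three places promise quality of life over time, and the schedule yields a single score at 6 months. No change or course can be estimated from it. What can be estimated, validly, is the difference between arms at 6 months, and that is how the outcome should be stated.

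The t test passes over baseline information already in hand. The benefit from using it is uncertain: residual variance falls by 9% to 49% for an assumed R of 0.3 to 0.7. The low end is plausible because the baseline scores are taken during an acute exacerbation and the outcome comes 6 months later.

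Severity is minor. One secondary outcome is affected, and antibiotic duration and the 14-day CCQ are untouched.

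**What to change.** 1. Delete *over time* from the CRQ-SAS outcome in Section 2, Section 10 and Appendix 5. Define it as the between-arm difference in CRQ-SAS score at 6 months, for the total and the four domains.
2. In Section 9, name CRQ-SAS and analyse it by linear regression of the 6-month score on arm, baseline CCQ and baseline EQ-5D-5L. State that these covariates are recorded before allocation is revealed, since Section 6.6.6 does not give the order.
3. If a diagram in the full document does show CRQ-SAS at enrolment, reconcile it with Sections 6.6.6 and 6.6.8.

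The cost is wording in three places, one analysis sentence and two covariates already collected. No new data are needed.

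Adding CRQ-SAS at enrolment or week 4 is optional. An enrolment form would give a direct baseline and allow change to be estimated, but it adds 17 items for acutely ill patients in a busy emergency department. It could also mix modes, because enrolment questionnaires are by interview and the 6-month form is sent for self-completion. A week 4 form alone would fall after randomisation and could not serve as a baseline.
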